8.3 TIME PERIOD AND FREQUENCY FOR EVENT ASSESSMENT AND FOLLOW-UP

All AEs and SAEs will be followed through resolution, stabilization, or until the subject is lost-to-follow-up.

The onset and end dates, duration, action taken regarding study drug, treatment administered, and outcome for each adverse event must be recorded on the CRF for randomized patients. The relationship of each adverse event to study procedures, and the severity and seriousness of each adverse event, as judged by the Investigator, must be recorded as described below.

8.4 REPORTING PROCEDURES

8.4.1 ADVERSE EVENT REPORTING

The study period during which AEs must be reported begins after informed consent is obtained and initiation of study treatment and for 5 days after randomization. Patients will be followed out to 90 days for death, ED utilization, and re-hospitalization as part of the study outcomes, which will also count as safety measures. Subject's hospital discharge summaries will be examined at hospital discharge and all non-exempt AEs will be investigated by examining necessary medical records.

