6.1.1 TREATMENT PROTOCOL

The algorithm below outlines the SSU AHF protocol.

Arm 1. SSU AHF Strategy: 'Short stay' is defined as < 24 hours. All SSU are monitored beds. Nursing ratios are similar to telemetry wards. Four principles of SSU AHF management are outlined: 1) relief of HF symptoms and signs; 2) decongestion while observing and correcting any electrolyte imbalances; 3) hemodynamic improvement; and 4) robust care transitions with an emphasis on guideline directed medication reconciliation and guideline recommended therapy at discharge.^{16,46} One potential advantage of the SSU AHF strategy is protocol driven care. (See Figure 3, next page) This figure is adapted from the ESC and SCPC Guidelines, primarily adding greater detail regarding vasodilator and diuretic dosing.⁴⁷ "Warm and wet" defines the HF phenotype from the Nohria et.al. classification: well perfused, volume overloaded.⁴⁸ The discharge criteria are taken from the SCPC guidelines on observation unit care.¹⁶

Arm 2. Usual care (defined by inpatient admission for AHF) was chosen as the comparator. In 2009, Dawson et.al. published the background framework for the 2005 NIH funded meeting on "Considering Usual Care in Clinical Trial Design: Scientific and Ethical Issues."⁴⁹ These principles informed our decision to use 'usual care' as the comparator.

One specific principle: consideration of ‘usual care’ when a comparator hypothesizes to be better than or equivalent to current clinical practice.⁴⁹ Hospitalization is the dominant strategy of care for over 80% of patients who present to the ED with AHF; thus, it provides the best real-world comparison of AHF care.⁵⁰ The median length of stay is 4.3 days.¹ We expect nearly all usual care patients to be cared for on general wards or telemetry and not ICU level of care, given our lower risk eligibility criteria. Guidelines are clear on suggested best practices for management.⁴⁹ Admittedly, the evidence supporting these statements in AHF are not as robust as chronic HF. This is one reason usual care has frequently been used in AHF therapeutic clinical trials.⁵¹⁻⁵³ Nevertheless, we will encourage guideline adherence in BOTH arms of the trial, both during hospitalization and pre-discharge. As hospitals are penalized on excessive 30-day readmissions, each participating hospital has a transitional care plan. In keeping with the pragmatic study design, each study arm will utilize their existing transitional care programs.

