7.3.3 FOLLOW-UP & FINAL STUDY VISIT

Patients will have follow up at 30 (+/- 7 days) days and 90 (+/- 30) days post-discharge (up to 120 total days after randomization is allowed if difficult to get a hold of a patient or more time is required to complete forms). There will be NO further in-person visits once discharged. However, treatment during hospitalization will be recorded. Patients will be called 30 days post-discharge ((+) 7 business days) and 90 days post-discharge (+/- 30 days) to assess vital status, re-hospitalizations or ED visits, as well as quality of life, caregiver burden, and resource utilization.

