7.3.7 SCHEDULE OF EVENTS TABLE

Schedule of Events Timepoint/Visit	Screen	Baseline	ARM 1 - PreDischarge from SSU	ARM 2 - PreDischarge from Hospital Floor	30-Day & 90 Day Follow up
Informed Consent	X				
Medical History		X			
Physical Exam		X	X	X	
Clinical lab tests*		X	X~	X~	
ECG*		X			
CXR*		X			
KCCQ (QoL) & SF-12			X	X	X
Oberst Caregiving Burden Scale and Bakas Caregiving Outcomes Scale			X	X	X ¹
HF Guideline Assessment			X	X	
Collect concomitant meds		X	X	X	
mRUQ-HF (resource utilization)					X ²
Cost Effectiveness Measures (i.e. DRG)					X
Guideline adherence assessment		X	X	X	X ¹
SCPC Discharge Criteria Adherence			X	X	
Assessment of AE/SAE's through 5 days			X	X	
Vital Status, ED visits, Hospital days, Re-admission status			X	X	X
Subject Payment			X	X	X ²

*per standard of care. Typical labs include: Na, K, renal function, HgB, troponin, Natriuretic Peptide levels. ~only if performed per usual care

SOC = standard of care, ED = Emergency Department, QoL = quality of life, HF = heart failure, mRUQ = modified resource utilization questionnaire, EMR = electronic medical record, DRG = diagnosis related group

¹Only through 30 days

²Sites may choose to make a single payment or to divide into 2 payments.

³only at 90 days

NOTE: If patients are hospitalized from the SSU, ONLY the following assessments should be collected. Otherwise, the pre-discharge assessments will apply.

- Physical exam
- Clinical lab tests
- Con meds
- SCPC discharge criteria. This would be conducted twice. Once in SCPS prior to hospitalization and again at discharge.

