8.1.1 DEFINITION OF ADVERSE EVENTS (AE)

The Investigator and study staff are responsible for detecting and recording AEs and SAEs during scheduled safety evaluations and whenever such information is brought to their attention. This section of the protocol provides definitions and detailed procedures to be followed. During each visit, the Investigator will question the patient about adverse events using an open question, taking care not to influence the patient's answers, e.g. "Have you had any unusual symptoms or medical problems since the last visit? If yes, please describe."

An AE is any unfavorable and unintended sign, symptom, or disease temporally associated with the use of an investigational (medicinal) product or other protocol-imposed intervention, regardless of attribution. It is expected that many HF patients will have events that are commonplace due to their HF and associated comorbidities. Our study plans to focus on AE that are outside of what is typically encountered during an AHF event and the subsequent 90 days.

This includes the following:

- AEs not previously observed in the subject that emerge during the protocol-specified AE reporting period (5 days for anything other than mortality, re-hospitalization, and ED visits)
- Complications that occur as a result of protocol-mandated interventions such as a medication adjustment
- Preexisting medical conditions (other than the condition being studied) judged by the investigator to have worsened in severity or frequency or changed in character during the protocol-specified AE reporting period that are outside of what would be expected for a patient with AHF or HF in the outpatient setting.

For example, a patient upgraded to ICU status from the observation or SSU. Hospitalization, by itself, does NOT count as it is expected to occur for a proportion of SSU patients.

- Abnormal laboratory values that fall into an abnormal range based upon the hospital's laboratory standards, the abnormality was not preexisting prior to enrollment, and the abnormality leads to a new treatment within the AE time frame, with the exception of repleting potassium.

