10.4.4 SAFETY ANALYSES

As all cause mortality and re-hospitalizations will already be reported as part of the efficacy exploratory analyses, these will also be highlighted as safety analyses. We will also report the proportion of patients who are admitted from the SSU as well as AE/SAE's.

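### Adverse events count for 5 days after randomization in both arms but are scheduled to be sought only until discharge, so between-arm AE counts can flatter the SSU arm

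*Combined protocol and SAP*

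**What the plan says.** **Reporting period.** Under 8.4.1, AE reporting "begins after informed consent is obtained and initiation of study treatment and for 5 days after randomization". Section 8.1.1 gives the same limit: "5 days for anything other than mortality, re-hospitalization, and ED visits". Neither section distinguishes the arms.

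**When AEs are sought.** In 7.3.7 the row "Assessment of AE/SAE's through 5 days" is marked in the two pre-discharge columns (SSU and hospital floor) and is blank under the 30- and 90-day follow-up. Section 8.1.1 has the investigator ask about AEs at each visit. Section 8.4.1 adds that "hospital discharge summaries will be examined at hospital discharge and all non-exempt AEs will be investigated by examining necessary medical records".

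**After discharge.** Section 7.3.3 states: "There will be NO further in-person visits once discharged". The telephone contacts are made "to assess vital status, re-hospitalizations or ED visits, as well as quality of life, caregiver burden, and resource utilization". AEs are not on that list.

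**Length of stay.** Section 6.1.1 defines a short stay as under 24 hours and gives a median of 4.3 days for usual care.

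**Use.** Section 10.4.4 says: "We will also report the proportion of patients who are admitted from the SSU as well as AE/SAE's". Death, ED use and re-hospitalization are followed to 90 days and also count as safety measures (8.1, 8.4.1).

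**The concern.** The reporting window is the same in both arms, but the scheduled search within it ends at discharge, and time to discharge is what the strategy is designed to change. Between discharge and day 5 no scheduled step looks for AEs, and SSU discharges spend most of the window in that gap. Laboratory-defined AEs follow the same pattern, because under 7.2.1 labs are drawn only as part of usual care.

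Premature discharge, from either setting, is the risk named in 2.3.1, and the first days at home are when some of its consequences could appear. If true AE risk were equal, recorded counts would tend to favour SSU, and a modest real excess could be hidden. Section 10.4.7 lets the DSMB recommend halting only for safety, on the totality of the data, so unevenly gathered AE counts could be read as evidence on that question.

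**Working it through.** The plan gives no figure for AE ascertainment, so there is nothing to reproduce. The check is how much of the 5-day window is under scheduled assessment in each arm.

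**Inputs**
- Window: 5 days (8.1.1, 8.4.1).
- SSU stay: at most 1 day (6.1.1); 1 day is used.
- Usual-care stay U: general median 4.3 days (6.1.1) and planning mean 5 days (10.5); or the risk-matched inpatient median of 58.5 h in 2.2, which is 58.5/24 = 2.44 days.
- Share of the SSU arm admitted, a: 40%, called conservative in 10.5. A value of 20% is my assumption.
- No AE learned of passively after discharge (assumption; it makes the result a bound).

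**1. Coverage by type of patient**
- SSU discharge: 1/5 = 20%.
- Usual care: 4.3/5 = 86%, or 2.44/5 = 49%.

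**2. Whole SSU arm, stays treated as fixed**

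Observed days = (1 − a) × 1 + a × min(5, 1 + U).

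| U | a | SSU arm, days | Ratio to usual care |
|---|---|---|---|
| 4.3 | 40% | 0.6 + 0.4 × 5 = 2.60 | 2.60/4.3 = 0.60 |
| 2.44 | 40% | 0.6 + 0.4 × 3.44 = 1.98 | 1.98/2.44 = 0.81 |
| 4.3 | 20% | 0.8 + 0.2 × 5 = 1.80 | 1.80/4.3 = 0.42 |
| 2.44 | 20% | 0.8 + 0.2 × 3.44 = 1.49 | 1.49/2.44 = 0.61 |

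**3. Stays allowed to vary**

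Take usual-care stay as lognormal with median 4.3 and mean 5, so sigma = √(2 ln(5/4.3)) = 0.549, and simulate 1,000,000 stays. Mean observed time, E[min(stay, 5)], is 3.92 days (78%) in usual care. In the SSU arm with 40% admitted it is 2.17 to 2.38 days; the lower value counts the SSU time within an admitted patient's stay, the higher adds it. The ratio is 0.55 to 0.61, or 0.40 to 0.43 with 20% admitted. With the median set to 58.5 h and the same sigma (an assumption), the ratio is 0.63 to 0.75, or 0.50 to 0.56 with 20% admitted.

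**4. Illustration on AE proportions**

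The documents give no AE rate. Assume a true 5-day risk of 10% in both arms and constant hazard h = −ln(0.9)/5. The recorded proportion is the mean of 1 − exp(−h × observed time), with 40% admitted.
- Median 4.3 days: 7.9% in usual care against 4.4 to 4.8% in SSU.
- Fixed stay of 58.5 h: 5.0% against 4.1%, a ratio of 0.81.
- True SSU hazard 1.5 times higher: 6.5 to 7.1% in SSU against 7.9% (median 4.3 days); 5.1 to 6.1% against 5.5% (median 58.5 h, varying stays). The excess is reversed in the first case and largely or wholly hidden in the second.
- Hazard halving each day, equal risk, median 4.3 days: 9.4% against 6.9 to 7.1%, so early clustering of events shrinks the gap but does not close it.

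With every patient assessed to day 5, coverage would be 5/5 in both arms and the artefact would vanish.

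**The case against.** **The serious harms are already captured.** A reader might infer that harm from early discharge goes unseen in the SSU arm, or that AEs and SAEs are equally biased. The documents do not support either. Death, ED visits and re-hospitalization are collected to 90 days in both arms, and time back in the ED or hospital enters the primary endpoint (10.4.2). Section 8.4.2 also speaks of following SAEs through day 30, though it does not say whether new ones are sought. What remains is AEs, and SAEs qualifying through disability or medical judgment (8.1.2) without one of those three outcomes. This limit stands.

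**The pool is narrower still.** Section 8.1.1 restricts AEs to those atypical for AHF, and 8.2.3 exempts many common events from regulatory reporting. The 10% risk above is therefore illustrative only.

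**Direction.** A reader might infer that the plan certainly flatters SSU. It need not: the specific reportable SAEs in 8.1.2 are listed for the SSU/OU arm only, and 8.1.1 uses ICU upgrade from the SSU as its example. Either may raise SSU counts. Conversely, the note to 7.3.7 limits assessments for patients hospitalized from the SSU to four items that omit AE/SAE; read strictly, this lowers SSU coverage further.

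**Size.** The 4.3-day figure describes AHF admissions generally. The risk-matched 58.5 h narrows the gap, though the direction of the observed-time ratio is unchanged. Passive capture (8.1.1) and the electronic record review listed in 5.3 would narrow it further by an unknown amount.

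**No test is planned.** Section 10.4.4 only reports AE/SAEs. True, but readers and the DSMB will set the arms side by side.

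**The calls might count as visits.** If so, the AE question in 8.1.1 would apply to them. The blank follow-up cells in 7.3.7 and the call content in 7.3.3 point the other way.

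**Conclusion.** The concern holds in a limited form. Scheduled AE ascertainment covers about 1 of 5 days for SSU discharges and about half to most of the window in usual care, so AE counts are not comparable between arms. The affected events are mainly AEs, and those SAEs that do not lead to death, an ED visit or re-hospitalization. For these, a between-arm reading can make SSU look safer than it is; this is likely, not certain.

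With 40% admitted from the SSU, the observed-time ratio is about 0.55 to 0.61 at a 4.3-day median and 0.63 to 0.81 at 58.5 h. With 20% admitted it is 0.40 to 0.56 with varying stays, and up to 0.61 with stays fixed at 58.5 h. These ratios assume no passive capture. They bound the bias and do not estimate it. The primary endpoint and the 90-day safety outcomes are unaffected.

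**What to change.** - **7.3.3 and 7.3.7:** add to the existing 30-day contact, in both arms, a short structured set of AE/SAE items and a record review covering randomization to day 5. State whether AE/SAE assessment continues for patients hospitalized from the SSU.
- **8.1.2:** apply the same list of specific reportable SAEs to both arms.
- **8.4.2:** say whether following SAEs through day 30 includes seeking new ones.
- **10.4.4:** report AE/SAEs over the full 5 days from the common source, split into in-stay and post-discharge. Give in-stay AEs per patient-day observed, using the stay times already captured for DAOOH (10.4.2). State that raw in-stay proportions will not be compared between arms.

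**Cost:** one form on a call already scheduled and a few lines of text; no change to sample size or the primary analysis. The drawback is imperfect recall of days 1 to 5 at about day 30, partly offset by record review. A contact or record review at day 5 in both arms would reduce the recall problem but adds a study step.

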8.4.2 SERIOUS ADVERSE EVENT REPORTING

All SAE's will be reviewed within 48 hours and all AE's within 7 days of discovery. SAE's will be followed through the entire follow up period (i.e. through day 30). Any SAE discovery will be reported to the DCC who will then report to the DSMB. If placebo treated patient, standard reporting to the IRB will occur. If active treated patient, and deemed to be related to drug, the SAE will be reported to the DSMB chair within 7 business days by email, fax, or phone of any fatal or life-threatening adverse event that is unexpected.

15 Calendar Day Written Report

The Investigator will also be required to notify the IRBs and all participating investigators, in a written Safety Report, of any serious, unexpected AE that is considered reasonably or possibly related to the strategy-of-care arm

72 hour reporting

For the discovery of an unexpected serious adverse event thought to be related to study procedures the Investigator(s) will notify the Chair of the DSMB by email within 72 hours.

8.5 STUDY HALTING RULES

Please see separate DSMB Charter

8.6 SAFETY OVERSIGHT

Please see separate DSMB Charter

9 CLINICAL MONITORING

Sites will be remotely monitored. Should the need arise for further investigation, an independent monitor will be appointed to visit sites. Each site has extensive clinical trial experience and the expectation for this need is low. Nevertheless, the PI will visit each site at least once per year for meeting with study staff and random surveillance.

10 STATISTICAL CONSIDERATIONS

10.1 STATISTICAL AND ANALYTICAL PLANS

Data Coordinating Center (DCC): The DCC will be housed at the Indiana University School of Medicine in the Department of Biostatistics, led by [name]. She will oversee data management and analysis related activities. The DCC will perform the following activities and functions:

- Overall responsibility for the biostatistics related to the trial. In this function, guidance and leadership will be provided regarding clinical trial methodology as well.

- Facilitate good study communication will be facilitated regarding trial progress and enrollment.
- Trial analysis and trial reports will be generated, including reports on the individual components of the study intervention – at both the site and overall study level – to ensure fidelity of each aspect of the study
- Database reports to monitor accrual as well as data quality, with queries generated to sites as needed
- Liaison with the DSMB and provide biostatistical support.
- Facilitate dissemination of the trial results through analysis and participation in the writing of study reports as well as manuscripts and presentations.
- Develop a Data Management Plan (DMP) in collaboration with participating sites of the study.
- Creation and maintenance of the eCRF
- Monitor patient enrollment and data collection by participating sites.
- Establish database lock procedures and clear change-control procedures for unlocking the database
- Produce protocol violation and deviation reports, missing data reports and data discrepancies reports will be generated. Automated edit checks both within and across CRFs and visit dates will be constructed by the DCC Data Manager. Queries generated will be forwarded by the DCC Data Manager to all participating sites' research coordinators for resolution.

10.1.1 ENDPOINTS AND RATIONALE

To ensure patient-centered endpoints, we twice met with patients and caregivers through two community engagement studios.⁵⁴ Patients prefer to be healthy and have a good QoL. If a safe alternative is available, patients prefer not to be hospitalized.

The **primary outcome** is **days alive and out of hospital (DAOOH) at 30 days post-randomization**. Unlike time-to-event analyses that ignores repeat events and gives equal weight to components of a composite endpoint,⁵⁵ DAOOH accounts for both frequency and duration of hospitalization and also weights mortality most heavily.^{55,56} This endpoint has also been suggested as a quality metric rather than re-hospitalization alone.⁵⁷

The **two secondary outcomes** are 1) **QoL using the KCCQ**. Patients desire not only to live longer, but to live better; or at minimum, not be worse after an acute health care related event.⁵⁸ Patients with advanced HF would trade survival time (or days alive) for a better QoL.⁵⁸ Our pilot work supports the feasibility of assessing QoL in the acute setting and suggests changes in scores are related to hospital re-visits.⁵⁹ We hypothesize that fewer days in the hospital in our SSU arm will also lead to a greater QoL. Interviews of hospitalized AHF patients suggest **they would prefer a shorter hospital stay or avoid an admission altogether**, assuming safety and outcomes are similar or better than hospitalization. Thus, assessing QoL is a key aim.

The KCCQ is a patient-reported, validated survey instrument designed to measure QoL in chronic HF patients.⁶⁰ Lower scores equal lower patient-reported QoL. **KCCQ scores predict adverse outcomes – namely hospitalization and mortality.** Importantly, the KCCQ demonstrates responsiveness to clinical change.⁶⁰⁻⁶²

A change of five points has been previously shown to be clinically significant, and will be assessed prior to discharge and day 30 post-randomization.⁶²

2) Cost effectiveness analysis, described in detail below.

NOTE: For patients randomized to SSU who worsen PRIOR to going to SSU, this will be counted the same as a hospitalization from the SSU.

ADDITIONAL ENDPOINTS

Adherence to guidelines saves lives and reduces hospitalizations and re-hospitalizations. We expect both the primary and secondary outcome will be affected by adherence to guidelines. Advances in medical therapy for HF patients with reduced ejection fraction (EF) prolongs life and decreases hospitalization.³⁹ Yet a substantial proportion of patients are

either not taking guideline-recommended medications or are on sub-optimal doses.^{63,64} We will emphasize and measure guideline adherence for eligible patients at the point of discharge from both study arms as well as during follow up.

Guideline adherence: the following HF measures will be assessed in **eligible** patients:^{47,65-67} (1) assessment of left ventricular function within a 12 month period, (2) use of angiotensin-converting enzyme inhibitor or angiotensin receptor blocker or ARNI (angiotensin receptor blocker/neprilysin inhibitor) for left ventricular systolic dysfunction (defined as an ejection fraction < 40%), (3) Use of guideline recommended Beta-blocker for left ventricular systolic dysfunction, (4) use of mineralocorticoid receptor antagonists (5) use of ivabradine (6) use of hydralazine/isosorbide dinitrate (7) provision of discharge instructions, (8) counseling for smoking cessation, and (9) follow up appointment provided within 7 days of discharge. A composite heart failure measure will be created by averaging all quality measures available per patient. Specifically, the *composite score* is defined as the total number of interventions performed divided by the total number of interventions for which the patient was eligible. In addition, we will assess for therapies prescribed inappropriately such as glitazones or ARNI prescribed simultaneously with an ARB.

Decreasing hospital stays may increase caregiver burden. Thus, we will also assess caregiver burden, using both the Oberst Caregiver Burden and Bakas Caregiver Outcome Scales, both validated instruments prior to discharge and again at 30 days.⁶⁸ Other measures of caregiver burden in HF have either not involved input from actual caregivers or missed important conceptual domains.⁶⁸ Effective caregivers has been associated with improved quality of life, lower hospitalization rates, and reduced mortality.^{68,69} As our primary focus is on the patient, the eligibility criteria for the caregiver will be broad, essentially including any person who after separate written informed consent, acknowledges themselves as the primary caregiver for the patient.

Out-of-pocket costs directly impact patients. As such, we will assess healthcare utilization from a societal perspective using the Modified Resource Utilization Questionnaire for Heart Failure (mRUQ-HF).⁷⁰ The mRUQ-HF is a 14-item self-report questionnaire of comprehensive lists of choice related to healthcare utilization. (See Appendix trial protocol) Exploratory analysis will occur in two steps: 1) Determination of resources consumed or related; 2) Assignment of 'value' to the resources consumed.⁷¹ This two-step process allows for transparency of assigned costs. Hospital costs will be assigned per individual hospital cost-accounting. Where monetary values are not directly self-reported, Medicare fee schedules will be used for uniformity.

